Appendix 5 Summary of Changes from Version 5.0 to Version 6.0

(Note: Administrative changes including minor administrative corrections are not included in Protocol Summary of Changes)

GRIFOLS Bioscience Industrial Group	Number GC2006 -A Multicenter, Randomized, Open-label, Parallel Group Pilot Study to Evaluate the Safety and Efficacy of Prostasin®-C Liquid plus Standard Medical Treatment (SMT) versus SMT alone in Hospitalized Subjects with	Version 6.0	Status Effective	Effective Date 08-Dec-2021	Page 92 of 94
Sections		Change From: (Version 5.0, dated 21 Jul 2021)	Change To: (Version 6.0)	Rationale:	
Synopsis, 2.6, 4.2, 9.1	New text for Interim Futility Analysis	
Interim Futility Analysis: An interim futility analysis will be conducted to assess whether the trial will be terminated due to lack of efficacy (futility) based on all available data assessable for the primary endpoint and key secondary efficacy endpoints.
		Addition of an interim futility analysis which will be conducted to provide guidance in the setting of dynamic changes within the context of an evolving epidemic.	
9.3	New section for Interim Futility Analysis	
An interim futility analysis will be conducted based on all available data assessable for the primary endpoint and key secondary efficacy endpoints to assess whether the trial will be terminated due to lack of efficacy (futility). The unblinded output will be reviewed by an independent unblinded team, and the study team will remain blinded.
 
Determination of futility from the interim futility analysis will be based on the conditional power (the power conditional on the observed data accumulated at the interim analysis) for the primary outcome, as well as assessment of the secondary efficacy outcomes.
 
The futility analysis will include for the primary efficacy endpoint variable, all patients with data through Day 29, and for the following secondary efficacy endpoint variables, all patients with data through Day 29, as specified for each endpoint:
 
Assessment of Clinical Severity: Change in NEWS from baseline (Day 1 through Day 29)
 
Time to clinical response: NEWS ≤ 2 maintained for 24 hours, Day 1 through Day 29
 
Time to hospital discharge: defined as duration of hospitalization from Day 1 through Day 29 (and duration of hospitalization)
 
If admitted to ICU post randomization: Duration of ICU stay through Day 29
 
Duration of any oxygen use Day 1 through Day 29
 
If requiring mechanical ventilation post randomization: Duration mechanical ventilation through Day 29
 
Absolute value and mean change from baseline
		Addition of an interim futility analysis which will be conducted to provide guidance in the setting of dynamic changes within the context of an evolving epidemic.	

GRIFOLS		Number	BIG-CL-PRT-000019	Version	6.0	Status	Effective	Effective Date	08-Dec-2021	Sections	Change From: (Version 5.0, dated 21 Jul 2021)	Change To: (Version 6.0)	Rationale:
Bioscience Industrial Group		GC2006 -A Multicenter, Randomized, Open-label, Parallel Group Pilot Study to Evaluate the Safety and Efficacy of Prolastin®-C Liquid plus Standard Medical Treatment (SMT) versus SMT alone in Hospitalized Subjects with											
8.5		Grifols will utilize a Study-Independent Safety Review Committee (SISRC) whose members (from Grifols) will be impartial and	Grifols will utilize a SISRC whose members (from Grifols) will be impartial and independent of the clinical trial team, and will consist of a global pharmacovigilance representative, a medical director, and a third individual knowledgeable in the epidemiological field or knowledgeable in the therapeutic area or a statistician.	Allowance for flexibility in areas of expertise for SISRC membership.									

GRIFOLS					
Number	Version	6.0	Status	Effective	Effective Date
GC2006 -A Multicenter, Randomized, Open-label, Parallel Group Pilot Study to Evaluate the Safety and Efficacy of Prostasin®-C Liquid plus Standard Medical Treatment (SMT) versus SMT alone in Hospitalized Subjects with					08-Dec-2021
Bioscience Industrial Group					
Sections		Change From: (Version 5.0, dated 21 Jul 2021)	Change To: (Version 6.0)		
		independent of the clinical trial team, and will consist of a statistician, global pharmacovigilance representative, and a medical director.			
			Rationale:

## SAP REVISIONS

Version 1.0 of the SAP was finalized based on Protocol version 4.0 (02 March 2021). The following table details subsequent changes made to the SAP to match protocol amendment.

Revision History			
SAP Version #	SAP Section	Modification	Description and Rationale
2.0	1	1) Changed protocol version from 4.0 to 6.0, and protocol date from 02 March 2021 to 08 December 2021.  2) Updated the last paragraph to "This document details the statistical methods planned to perform the interim safety and futility, as well as the final analyses of the study".	1) and 2) Updated to match the protocol amendment.
2.0	3.1	Added the language for interim futility analysis.	Updated to match the protocol amendment.
2.0	6.1 and 6.2	Changed Fisher's exact method to Chi-square statistic.	Changed to reflect the planned analysis.
2.0	8	1) Added a section number and title "8.1 Interim Safety Analysis" for safety interim analysis.  2) Added Section 8.2 for interim futility analysis.	1) Clarify the original section is about Safety interim analysis.  2) Interim futility analysis was added to the protocol amendment, updated to match the protocol v6.0 and to provide the details of conditional power calculation.

## LIST OF ABBREVIATIONS

Abbreviation	Definition
ADR	Adverse drug reaction
AE	Adverse event
Alpha1-PI	Alpha 1-Proteinase Inhibitor
ANOVA/ANCOVA	Analysis of variance/covariance
ARDS	Acute respiratory disease syndrome
ATC	Anatomical, Therapeutic, and Chemical
BMI	Body mass index
CDF	Cumulative distribution function
CI	Confidence interval
CIF	Cumulative Incidence Function
COVID-19	Coronavirus disease 2019
CP	Conditional power
eCRF	Electronic Case Report Form
CRP	C-reactive protein
ECMO	Extracorporeal Membrane Oxygenation
FEU	Fibrinogen Equivalent Units
ICU	Intensive care unit
IgG	Immunoglobulin G
IgM	Immunoglobulin M
IL	interleukin
IP	Investigational product
ITT	Intention to treat
IV	Intravenous
KM	Kaplan-Meier
LS	Least-Squares
MedDRA	Medical Dictionary for Regulatory Activities
MMRM	Mixed-effects model for repeated measures
NAT	Nucleic acid amplification technology
NEWS	National Early Warning Score

Abbreviation	Definition
PCR	Polymerase chain reaction
PI	Principal Investigator
PP	Per-Protocol
PT	Preferred term
RT-PCR	Reverse transcriptase PCR
SAE	Serious adverse event
SAF	Safety
SAP	Statistical analysis plan
SARS-CoV-2	Severe acute respiratory syndrome coronavirus 2
SMT	Standard medical treatment
SOC	System organ class
SaO 2	Arterial oxygen saturation
SpO 2	Oxygen Saturation by pulse oximetry
TEAE	Treatment-emergent adverse event
TNF- $\alpha$	tumor necrosis factor- $\alpha$
WHO	World Health Organization

## **1. INTRODUCTION**

This statistical analysis plan (SAP) is based on the Protocol # GC2006 Version 6.0, dated 08 December, 2021, and titled “A Multicenter, Randomized, Double-blind, Placebo-Controlled, Parallel Group Study to Evaluate the Safety and Efficacy of Liquid Alpha1-Proteinase Inhibitor (Human) plus Standard Medical Treatment (SMT) versus Placebo plus SMT in Hospitalized Subjects with COVID-19.” See the study protocol for full details.

This document details the statistical methods planned to perform the interim safety and futility, as well as the final analyses of the study.

## **2. OBJECTIVES AND ENDPOINTS**

### **2.1 Objectives**

#### **2.1.1 Primary Efficacy Objective**

To determine if Liquid Alpha1-Proteinase Inhibitor (Human) (Liquid Alpha1-PI) plus SMT can reduce the proportion of subjects dying or requiring intensive care unit (ICU) admission on or before Day 29 or who are dependent on high flow oxygen devices or invasive mechanical ventilation on Day 29 versus placebo plus SMT in hospitalized subjects with COVID-19.

#### **2.1.2 Secondary Efficacy Objectives**

To compare Liquid Alpha1-PI plus SMT versus placebo plus SMT with regard to clinical efficacy as assessed by clinical severity, duration of hospital stay, dependency on oxygen or new need for ventilatory support, clinical response criteria including National Early Warning Score (NEWS) and clinical status scale through Day 29 in hospitalized subjects with COVID-19.

#### **2.1.3 Exploratory Efficacy Objectives**

The exploratory objectives of the study are:

- To evaluate the effect of Liquid Alpha1-PI (Human) plus SMT versus placebo plus SMT with regard to quantitative severe acute respiratory syndrome, coronavirus 2 (SARS-CoV-2) viral load and anti-SARS-CoV-2 antibodies in hospitalized subjects with COVID-19.
- To evaluate whether Liquid Alpha1-PI (Human) plus SMT versus placebo plus SMT reduces the frequency of hyperinflammation based on a pre-specified biochemical definition through Day 29.
- To evaluate cytokine profile changes from baseline for Liquid Alpha1-PI (Human) plus SMT versus placebo plus SMT through Day 29.
- To evaluate levels of alpha1-proteinase inhibitor (alpha 1-PI, also known as alpha 1-antitrypsin [AAT]) activity and antigen through Day 29 (samples to be stored for measurement of both antigenic content and functional activity [potency] assays)

#### **2.1.4 Safety Objective**

To determine the safety and tolerability profile through Day 29 of Liquid Alpha1-PI (Human) plus SMT versus placebo plus SMT in hospitalized subjects with COVID-19.

## 2.2 Endpoints

### 2.2.1 Primary Efficacy Endpoint

The primary efficacy endpoint is the proportion of subjects dying or requiring ICU admission on or before Day 29 or who are dependent on high flow oxygen devices or invasive mechanical ventilation on Day 29.

### 2.2.2 Secondary Efficacy Endpoints

The secondary efficacy endpoints include the following:

- Assessment of Clinical Severity: Change in NEWS from baseline (Day 1 through Day 29).  
The NEWS has demonstrated an ability to discriminate patients at risk of poor outcomes. This score is based on 7 clinical parameters (respiration rate, oxygen saturation, any supplemental oxygen, temperature, systolic blood pressure, heart rate, level of consciousness [Alert, Voice, Pain, Unresponsive]).
- Time to clinical response: NEWS  $\leq 2$  maintained for 24 hours, Day 1 through Day 29
- Time to hospital discharge: defined as duration of hospitalization from Day 1 through Day 29
- If admitted to ICU post randomization: Duration of ICU stay through Day 29
- Duration of any oxygen use Day 1 through Day 29
- If requiring mechanical ventilation post randomization: Duration mechanical ventilation through Day 29
- Absolute value and mean change from baseline in the Ordinal scale Day 1 through Day 29  
The Ordinal scale is as follows:
  - 1) Death;
  - 2) Hospitalized, on invasive mechanical ventilation or extracorporeal membrane oxygenation (ECMO);
  - 3) Hospitalized, on non-invasive ventilation or high flow oxygen devices;
  - 4) Hospitalized, requiring supplemental oxygen;
  - 5) Hospitalized, not requiring supplemental oxygen;
  - 6) Not hospitalized, limitation on activities;
  - 7) Not hospitalized, no limitations on activities.
- Proportion (percentage) of subjects in each severity category of the 7-point Ordinal scale at Day 15 and Day 29
- Time to sustained normalization of temperature and proportion of subjects with normalization of fever at all time points, defined as temperature  $<36.6$  °C armpit,  $<37.2$  °C oral, or  $<37.8$  °C rectal sustained for at least 24 hours
- Number of subjects who develop Acute Respiratory Distress Syndrome (ARDS) through

Day 29

- Length of time to clinical progression through Day 29 (defined as the time to death, mechanical ventilation, or ICU admission)

### 2.2.3 Exploratory Efficacy Endpoints

The exploratory efficacy endpoints include:

- Change from baseline in quantitative SARS-CoV-2 viral load by nucleic acid amplification technology (NAT) or polymerase chain reaction (PCR; real-time reverse transcriptase [RT]-PCR) to Day 5± 1, Day 15± 1, and Day 29± 1
- Change from baseline in quantitative anti- SARS-CoV-2 immunoglobulin M (IgM) and IgG antibodies to Day 5± 1, Day 15± 1, and Day 29± 1
- Proportion of subjects with evidence of hyperinflammation on Day 1, Day 5, Day 15, and Day 29 defined as:
  - Lymphocyte counts <1000 cells/µL, AND
  - Two of the following 4 criteria:
    - Ferritin > 500ng/mL,
    - LDH > 300 U/L,
    - D-Dimers > 1000 ng/mL (fibrinogen equivalent units [FEU]) or > 2 times upper normal limit,
    - C-reactive protein (CRP) > 70 mg/L
- Change from baseline in cytokine profile (cytokine panel includes interleukin (IL)-1 $\beta$ , IL-10, IL-6, IL-8 IL-2, interferon  $\gamma$ , and tumor necrosis factor- $\alpha$  [TNF- $\alpha$ ]) to Day 5± 1, Day 15± 1, and Day 29± 1
- Change from baseline in levels of alpha 1-PI (AAT) activity and antigen through Day 29 (both plasma [sodium citrate] and serum samples to be stored for measurement of both antigenic content and functional activity [potency])

### 2.2.4 Safety Endpoints

The safety endpoints include:

- Cumulative incidence of treatment-emergent serious adverse events (SAEs) and potentially related SAEs through Day 90 phone check
- Cumulative incidence of Grade 3-5 treatment-emergent adverse events (TEAEs) and potentially related TEAEs through Day 29 as defined in the Common Terminology Criteria for Adverse Events (CTCAE), US Department of Health and Human Services, National Institutes of Health (NIH), and National Cancer Institute (NCI)
- Cumulative incidence of all TEAEs and potentially related TEAEs through Day 29

### 3. INVESTIGATIONAL PLAN

#### 3.1 Study Design

This is a prospective, multi-center, randomized, double-blind, placebo-controlled study of Liquid Alpha1-PI (Human) plus SMT versus placebo plus SMT in subjects with COVID-19 who are hospitalized. The first 6 subjects randomized will be staggered with an interval of no less than 1 week between subjects. If there are no definitely related SAEs reported by the time Day 8 is completed by the 6th subject, competitive enrollment would ensue thereafter. If a definitely related SAE were to be reported among these 6 subjects, and the subject was found by the Study-Independent Safety Review Committee (SISRC) to be randomized to the Liquid Alpha1-PI (Human) plus SMT arm, the SISRC would carefully review and evaluate the case and make appropriate recommendations with regard to study status.

In this study, symptomatic subjects with positive PCR (RT-PCR), NAT for SARS-CoV-2 (or other commercial or public health assay approved by regulatory authorities) will receive placebo plus SMT or SMT plus Liquid Alpha1-PI (Human) given as two intravenous (IV) doses of 120 mg/kg (body weight) one week apart (on Day 1 and Day 8); if the subject is discharged from the hospital then the 2nd infusion is not mandatory, and is at the discretion of the Principal Investigator (PI) and subject.

[figure not shown]
Specifically, subjects randomized to combination Liquid Alpha1-PI (Human) will receive the first IV infusion of blinded Liquid Alpha1-PI (Human) (120 mg/kg body weight) or Placebo on Day 1. A second Placebo/ Liquid Alpha1-PI (Human) dose of 120 mg/kg body weight will be administered a week later on Day 8. if the subject has been discharged from the hospital at the time of the Day 8 blinded Placebo/ Liquid Alpha1-PI (Human) infusion, the 2nd infusion is not mandatory, and is at the discretion of the PI and subject.

Approximately 100 subjects (who meet the inclusion/exclusion criteria specified in Protocol Sections 5.1 & 5.2) will be randomized in a 1:1 [Liquid Alpha1-PI (Human) plus SMT : Placebo plus SMT] ratio with an interim analysis after 50 subjects (approximately 25 per group). There will be no interruption in study conduct during interim analysis as this simply represents sponsor safety due diligence during the COVID-19 pandemic. An interim futility analysis will be conducted to assess whether the trial will be terminated due to lack of efficacy (futility) based on all available data assessable for the primary endpoint and key secondary efficacy endpoints.

All subjects will be followed daily through Day 10 (note: for Day 6 through Day 10, this stipulation is for as long as subjects are hospitalized). After Day 6, if subjects are discharged from the hospital, evaluations at Day 15 and 29 are required. Subjects remaining hospitalized will be followed daily through Day 29. Phone Checks will occur at Day 60 and Day 90 for vital status (living or deceased), any hospital re-admissions or serious/non-serious AEs after the Day 29 Final Clinic Visit. See Appendix A for the Schedule of Events.

Clinical trial finalization will coincide with the last study visit of the last subject enrolled in the clinical trial. For an individual subject, end of study for the purposes of determining disposition and successful study completion is the Day 29/Final Clinic Visit performed at the scheduled on-study timeframe.

An overview of the study design is presented below:

IV = intravenous; SMT = standard medical treatment

\*Note: If the subject has been discharged from the hospital at the time of the Day 8 blinded Liquid Alpha-1 PI infusion, the 2nd infusion is not mandatory, and is at the discretion of the Principal Investigator and subject

## 3.2 Treatment

### 3.2.1 Randomization Scheme and Treatment Arm Assignment

Subjects will be randomized 1:1 to receive either combination treatment with Liquid Alpha1-PI (Human) plus SMT or placebo plus SMT.

### 3.2.2 Blinding

The unblinded study pharmacist or designee will be the only unblinded study person at each site. Preparation and pooling of study drug [Liquid Alpha1-PI (Human) and placebo] will be the responsibility of the local unblinded pharmacist or designee.

### 3.2.3 Dosing Schedule

During this clinical trial, subjects randomized to receive combination Liquid Alpha1-PI (Human) plus SMT will receive the first dose of blinded Liquid Alpha1-PI (Human) given as an IV dose of 120 mg/kg (body weight) on Day 1. A second dose of blinded Liquid Alpha1-PI (Human) (120 mg/kg) will be infused on Day 8. If the subject has been discharged from the hospital at the time of the Day 8 blinded Liquid Alpha1-PI (Human) infusion, the 2nd infusion is not mandatory, and is at the discretion of the PI and subject.

### 3.2.4 Treatment Compliance

Reasons for any deviation from the administration of less than 100% of the investigational product (IP) dose must be recorded in the subject's medical records.

The investigator or designee is responsible for maintaining accurate records of study medication administered at his/her study center.

## 4. GENERAL CONSIDERATIONS FOR DATA ANALYSIS

Unless otherwise specified, continuous variables will be summarized using descriptive statistics

(n, mean, standard deviation, median, minimum, and maximum). Categorical variables will be summarized showing the number and percentage of subjects within each category.

Summary results will be provided for each treatment group. All tabulations will be based on pooled data across centers.

All statistical tests will be two-sided and tested at the 5% level of significance.

Analyses will be performed using SAS for Windows statistical software, version 9.4 or higher (SAS, Cary, NC), except where other software may be deemed more appropriate. In the event that other software is used to perform some analyses, the details will be provided in the Clinical Study Report.

██████████ will perform all efficacy and safety analyses described in this SAP and Grifols will review them.

Subject data will be listed, sorted by treatment group and subject number. When applicable, listings will be additionally sorted by visit and assessment date/time.

#### **4.1 Data Quality Assurance**

Once all the source verification is complete, all queries are resolved, and the database has been updated appropriately, the database will be locked and made available to █████ Biostatistics for final analysis.

Data may be pulled by █████ Biostatistics for interim analyses at a time when source verification and query resolution is ongoing.

All SAS programs used to create analysis data sets, tables, and listings are double programmed. The SAS outputs will be compared and the programs will be updated until the outputs match.

#### **4.2 Analysis Populations**

The following three analysis populations will be defined for this study:

The intent-to-treat (ITT) population is defined as all subjects who are randomized. All efficacy analyses will be carried out using the ITT population based on the randomized treatment.

The Per-Protocol (PP) population is defined as the subset of subjects included in the ITT population who do not present major protocol deviations which might have an impact on the primary efficacy endpoint, and complete at least 80% of the IP. The primary efficacy analyses will be carried out using the PP population if different from the ITT population.

The Safety (SAF) population is defined as the subset of subjects who receive at least any amount of Liquid Alpha1-PI (Human) plus SMT or placebo plus SMT. All safety analyses will be carried out using the SAF population based on the treatment actually received rather than randomized treatment.

The validity of a subject for inclusion in each of these populations (ITT, Safety, and PP) will be assessed before unblinding the database and documented in a blinded review report.

#### **4.3 Assessment Windows**

Data will be summarized by nominal study visit recorded in the database.

#### 4.4 Handling of Dropouts or Missing Data

Missing data will be treated as missing and no method for imputation is planned for study population or safety analyses except for the partial end dates/times for concomitant medications (Section 5.6) and partial onset dates/times for AEs (Section 7.2.1). When applicable, missing data for binary and selected continuous efficacy endpoints will be imputed using a most conservative/worst case approach, and the related details are described in Section 6.

Time to event endpoints will have events coded as right censored or competing events per the following table:

**Table 1 Missing Data and Competing Events Coding for Time to Event Data Analyses**

Endpoint	Right Censoring and Competing Events
Time to Clinical Response	Subjects who did not experience clinical response or died at any time during follow-up will be right censored as of the date of last non-missing assessment of NEWS on or prior to Day 29.
Time to Hospital Discharge	Subjects who did not discharge from the hospital at any time during follow-up will be right censored as of the date of last subject contact when the subject was known to be in the hospital. Subject death will be considered a competing event. Competing risk methods e.g., cumulative incidence function (CIF) will be used to account for competing events in the analysis.
Time to Sustained Normalization of Temperature	Subjects who did not meet the criteria for sustained normalization of temperature or died at any time during follow-up will be right censored as of the date of last non-missing assessment of temperature on or prior to Day 29.
Time to Clinical Progression (death, mechanical ventilation, or ICU admission)	Subjects who did not meet the criteria for clinical progression will be right censored as of the date of last subject contact on or prior to Day 29.

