#### 4.6 Data Derivations and Transformations

The following derivations will be used in this study:

Study Day:

- Date of assessment – 1st date of study drug administration + 1 for assessments done on or after the 1st date of study drug administration
- Date of assessment – 1st date of study drug administration for assessments done before the 1st date of study drug administration

Baseline Observation: the last non-missing value prior to the 1st study drug administration.

Duration:

- Duration in days = end date – start date + 1
- Duration in minutes = end time in minutes – start time in minutes

Origin or Start Date for Time to Event Endpoints:

- Time to Clinical Response: date of 1st study drug administration
- Time to Hospital Discharge: date of 1st study drug administration
- Time to Sustained Normalization of Temperature: date of 1st study drug administration
- Time to Clinical Progression: date of 1st study drug administration

Event Date for Time to Clinical Response and time to sustained normalization of temperature:

- If a subject met the criteria for clinical response or sustained normalization of temperature at multiple assessments, the date of the first assessment meeting the definition of clinical response or sustained normalization of temperature will be used as the event date for deriving time to clinical response or sustained normalization of temperature.

Event Date for Time to Clinical Progression

- The event date will be the date of death, the start date of mechanical ventilation, or the date of ICU admission, whichever occurs first.

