### **Time to clinical response**

Clinical response is defined as the NEWS score <=2 maintained for 24 hours from Day 1 through Day 29. The time to the first occurrence of clinical response will be estimated using the Kaplan-Meier (KM) method. The KM estimates along with 95% CI, and survival curves will be provided. Based on the KM estimates, the probabilities of achieving first clinical response and associated 95% CIs on Days 15 and 29 will be reported; in addition, the 25th, 50th (median), and 75th percentiles of the time to first clinical response with associated 95% CIs will be provided, as data permit. The survival rates between treatment groups will be compared using Log-rank test. The p-value from Log-rank test will be presented.

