### **Time to hospital discharge**

Time to hospital discharge is defined as duration of hospitalization from Day 1 through Day 29. The proportion of subjects who are discharged from the hospital will be estimated using the CIF. Deaths that occur prior to discharge from the hospital will be treated as a competing risk. The estimated cumulative incidence and associated two-sided 95% CI on Days 15 and 29 will be displayed. Test for equality of the CIF between treatment groups will be conducted using Gray's test.

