### **Sustained normalization of temperature**

Sustained normalization of temperature is defined as the temperature  $<36.6$  °C armpit (axillary),  $<37.2$  °C oral, or  $<37.8$  °C rectal sustained for at least 24 hours through Day 29.

- The time to the first occurrence of sustained normalization of temperature will be estimated using the KM method. The KM estimates along with 95% CI, and survival curves will be provided. Based on the KM estimates, the probabilities of achieving first sustained normalization of temperature and associated 95% CIs on Days 15 and 29 will be reported; in addition, the 25th 50th (median), and 75th percentiles of the time to first sustained normalization of temperature with associated 95% CIs will be provided, as data permit. The survival rates between treatment groups will be compared using Log-rank test. The p-value from Log-rank test will be presented.
- The proportion of subjects who have experienced sustained normalization of temperature at any timepoint through Day 29 within each treatment group will be presented along with a two-sided exact (Clopper-Pearson) 95% CI.

The observed difference in the proportion of subjects who achieved sustained normalization of temperature at any timepoint between treatment groups along with the exact unconditional 95% CI for risk difference will be calculated. The null hypothesis of no between-treatment difference will be tested using Chi-square statistic and the p-value will be reported.

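### As worded, two rows of SAP Table 1 censor subjects who die after responding, although SAP 4.6 and 6.2 count the first response as the event

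*SAP*

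**What the plan says.** SAP 4.4, Table 1, gives the coding for time to clinical response: "Subjects who did not experience clinical response or died at any time during follow-up will be right censored". The censoring date is the last NEWS assessment no later than Day 29. The row for temperature has the same structure: "Subjects who did not meet the criteria for sustained normalization of temperature or died at any time during follow-up will be right censored".

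SAP 4.6 defines the event date for both endpoints. If the criteria are met more than once, "the date of the first assessment meeting the definition of clinical response or sustained normalization of temperature will be used as the event date". It sets no condition on later survival.

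SAP 6.2 analyses the first occurrence in each case: "The time to the first occurrence of clinical response will be estimated using the Kaplan-Meier (KM) method" and "The time to the first occurrence of sustained normalization of temperature will be estimated using the KM method". Both use a log-rank comparison.

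For time to hospital discharge, SAP 6.2 does state the order of events: "Deaths that occur prior to discharge from the hospital will be treated as a competing risk".

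**The concern.** Table 1 joins two groups with an unqualified 'or': subjects without the event, and subjects who died. The second group includes anyone who had already met the criteria and died afterwards. For that subject Table 1 and SAP 4.6/6.2 give different records, and the SAP states no order of precedence.

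Two things follow if Table 1 is programmed as worded. A later outcome removes an event that was observed, and the subject stays in the risk set after responding. If mortality differs between arms, part of that difference then appears as a difference in speed of NEWS or fever recovery, even where that speed is the same. SAP 6.2 also reports the proportion with sustained normalization at any time through Day 29. The same subject would count as a success there and as censored in the Kaplan-Meier analysis of the same criterion.

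**Working it through.** The plan has no figure to reproduce: it gives no event rate, mortality or power for these endpoints. The check sets the rules side by side and then sizes the difference under stated assumptions.

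**One subject.** Response on Day 6, last NEWS on Day 19, death on Day 20 (invented for illustration).
- SAP 4.6 and 6.2: time 6, event.
- Table 1 as worded: time 19, censored.

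One event is lost, and the subject stays at risk for 19 − 6 = 13 days after responding.

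**One arm, fixed data.** Assume 50 subjects, 40 first responses on Days 3-14, and 10 non-responders censored at Day 29. Let k responders die later, each with a last NEWS on Day 20. No censoring precedes the last event, so the Day 29 Kaplan-Meier response is (number of events)/50.
- First-event rule: 40/50 = 0.80 for any k.
- Table 1 as worded: (40 − k)/50, which is 0.78, 0.76, 0.74 and 0.70 for k = 1, 2, 3 and 5.

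Each such death costs 1/50 = 2 percentage points. With identical response times in both arms, the log-rank z moves from 0 to 0.44 (p = 0.66) for 1 vs 3 later deaths, 0.81 (p = 0.42) for 1 vs 5, and 1.09 (p = 0.28) for 0 vs 5.

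**Simulated trials.** From the SAP: about 100 subjects randomized 1:1, so 50 per arm, and two-sided 5% tests. Assumed: median 4 days to event in both arms, deaths spread evenly over about Days 5-28, and a given share of fatal cases able to reach the event before death. Deaths without a prior event are censored at the last assessment under both rules, so only deaths after the event are coded differently.

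| Mortality | Fatal cases able to reach event | Rejection, first-event rule | Rejection, Table 1 as worded |
|---|---|---|---|
| 20% vs 10% | 70% | about 7% | about 17% |
| 20% vs 10% | 30% | about 13% | about 19% |
| 20% vs 10% | 10% | about 16% | about 19% |
| 10% vs 5% | 70% | about 6% | about 9% |
| 15% vs 15% | 70% | 5-6% | 5-6% |

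Repeat runs of this set-up moved individual entries by up to about two percentage points.

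The number recoded follows from the assumptions. At 20% vs 10%, expected deaths are 50 × 0.20 + 50 × 0.10 = 15. At 70%, 15 × 0.70 = 10.5 could reach the event, and about 9 do so before dying. At 10% the ceiling is 15 × 0.10 = 1.5, and about 1.3 are recoded. With equal mortality the test is unaffected, but the Day 15 Kaplan-Meier estimate falls by about 8 points in both arms (0.89 to 0.81).

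**The case against.** The strongest reply is that context settles the meaning. Table 1 sits under the handling of dropouts and missing data, so it is there to code subjects whose event was not observed, and a responder who later dies has an observed event. The discharge row of the same table is equally unqualified about death, and SAP 6.2 then limits it to deaths before discharge. Table 1 may simply be shorthand. This stands as evidence of intent: the authors probably meant deaths without a prior event. It does not remove the conflict, because SAP 6.2 supplies a limit for discharge and none for response or temperature.

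A reader might go further and infer that deaths learned at the Day 60 or Day 90 calls would also undo a response. The documents do not establish this. Protocol 4.2 ends its phase of observation and follow-up at Day 29 and lists the phone checks separately, and a subject's end of study is Day 29. Usage elsewhere is looser: the synopsis calls the phone checks follow-up of vital status. The point is best confined to deaths through Day 29, with the later ones left as an ambiguity that the rewording also closes.

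The size is also open to challenge, and that challenge stands in part. A 70% chance of reaching the event before death is doubtful for NEWS. Under Protocol Appendix 2, supplemental oxygen alone scores 2, so a subject on oxygen must score zero on every other item for 24 hours. It is more plausible for temperature, because the inclusion criteria do not require fever. When few fatal cases reach the event, most of the excess rejection comes from deaths without a prior event, which is a different question.

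**Conclusion.** The wording of the clinical-response and temperature rows of Table 1 is wrong as written and conflicts with SAP 4.6 and 6.2 for subjects who meet the criteria and then die. This is a drafting defect with two possible codings. It is not proof that the sponsor intends to discard responses; that stronger reading is one a literal programmer could adopt, and the rest of the SAP argues against it.

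It affects two secondary endpoints in a study that calls itself exploratory. The primary endpoint has its own derivation in SAP 6.1 and is untouched. The two endpoints do enter the futility review in SAP 8.2, beside conditional power and other outcomes.

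The size depends on unstated rates. At 20% vs 10% mortality the excess rejection from the Table 1 coding is about 10 percentage points (17 − 7) if 70% of fatal cases can reach the event first, 6 points (19 − 13) at 30%, and 3 points (19 − 16) at 10%. At 10% vs 5% mortality it is about 3 points (9 − 6) even at 70%. A large effect needs both frequent recovery before death and a wide mortality gap.

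**What to change.** Reword the two rows and keep the censoring date that they now state (for response, "right censored as of the date of last non-missing assessment of NEWS on or prior to Day 29"), since it is the only one given for these endpoints. Suggested text:

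*Subjects who have not met the criteria by Day 29, including those who die without having met them, are right censored at their last non-missing NEWS (temperature) assessment no later than Day 29. A subject who met the criteria before death has an event on the date of the first qualifying assessment.*

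This agrees with SAP 4.6 and 6.2 and makes deaths after Day 29 irrelevant to the coding. It leaves open whether a death without a prior event should be censored or treated as a competing event, as it is for discharge; that should be decided separately. The cost is two table rows and the matching program specification, with no new data. It should be done before the unblinded futility output is produced.
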